Pilot study of PK parameters in an adult CF cohort with APE: We assayed steady-state pharmacokinetic and pharmacodynamic properties of intravenous colistin in CF subjects >18 years old admitted for APE treatment, during the first week of admission. The primary objective of the study was to determine PK parameters, specifically clearance (CL), volume of distribution (VD), area under the curve (AUC), and maximal concentrations (Cmax). A total of 16 CF subjects were evaluated. All subjects received IV colistin on a standard dosing schedule, in conjunction with other anti-Pseudomonal antibiotic agents, dosed three times daily. Patient characteristics are depicted in Table 1. Steady state plasma concentrations were obtained after \geq 2 days of therapy during week 1 of admission, and subjects underwent phlebotomy at 0, 0.5, 1, 2, 4, and 6 hours after administration. Peak, midpoint, and trough colistin A and B concentrations (active drug) were measured utilizing liquid chromatography-mass spectrometry (LC-MS) technology^{21,22}. As seen in Table 1, the mean study age of 32 is older than mean ages in prior studies of IV colistin in CF subjects^{19,20}. Mean FEV₁ % predicted was 40% predicted at onset of exacerbation, demonstrating that the drug can be given safely with severe airflow limitation. There were no reported side effects of chest tightness that would limit its use. Two subjects experienced SCr rises of \geq 0.3 mg/dL, necessitating discontinuation of drug. Mean colistin dosing was 3.42 mg/kg/d over 15 days. A PK analysis of

Table 1: Characteristics of colistin PK pilot study subjects

No. of subjects	16
Gender- no. (% female)	8 (50)
Age (mean \pm SD years)	32 \pm 13
Sputum culture	
Pseudomonas aeruginosa only	8 (50)
Pseudomonas aeruginosa, Staphylococcus aureus, and/or other GNR	8 (50)
Concomitant systemic antibiotic therapy- no. (%)	
β -lactam, carbapenem, monobactam, or quinolone	16 (100)
vancomycin or linezolid	5 (31)
FEV ₁ (mean \pm SD % predicted)	40 \pm 15
Mean dose colistin- mg/kg/d (mean \pm SD)	3.42 \pm 0.6
Mean duration of therapy-days (mean \pm SD)	15 \pm 9
Baseline SCr- mg/dL (mean \pm SD)	.77 \pm .27
Number with AKI (% with $>$ 0.3 mg/dL increase in SCr)	2 (13)
SCr- serum creatinine	
AKI- acute kidney injury	

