Retrospective efficacy and safety of standard IV colistin dosing in a large CF inpatient population. We retrospectively analyzed IV antibiotic courses for treatment of CF APE amongst patients of the Denver Adult CF Program from 2012-2015. Greater than 240 courses of colistin were administered to 240 adult subjects, and >350 courses of tobramycin in 350 subjects. A dataset of admissions with complete data (n=465) was analyzed for FEV₁ improvement based on treatment with tobramycin or colistin and for the development of acute kidney injury (AKI) based on an absolute increase of serum creatinine by ≥ 0.3 mg/dl²⁷. Subjects received on average a course of 14.6 days of colistin during APE treatment versus 12.7 days of tobramycin. The average ages of subjects receiving tobramycin and colistin were 31 and 32 years old respectively. The tobramycin group was 57% female, while the colistin group was 60% female. The colistin group consisted of 66% CFRD diagnosed patients, while the tobramycin group had 38% with CFRD. More admissions occurred for the colistin group (average of 2.3/year), versus the tobramycin group, which underwent an average of 1.8 admits per year. Pre-treatment FEV₁ % predicted ranged higher for the group receiving tobramycin (average of 50%), versus the colistin group (average of 40% predicted), reflecting a sicker population receiving intravenous colistin. Of interest, the degree of FEV₁ improvement before and after APE treatment was 12% predicted with tobramycin versus 9% predicted for colistin (p=0.006). However, the small increase in FEV₁ improvement came at a price, since the incidence of AKI was 19% for the tobramycin group and 12% for the colistin group, giving an OR of 3.6 for tobramycin (p=0.002). The analysis was adjusted for prior year admissions, reflecting the reality that CF subjects receive multiple IV antibiotic courses over sequential years. Since mounting evidence

demonstrates that AKI occurrences, defined as a creatinine rise by ≥ 0.3 mg/dL, are associated with increased morbidity, higher one year mortality, and chronic kidney disease, the fact that patients experience this endpoint not infrequently, and repeatedly, is meaningful^{28,29}.

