3. STUDY OBJECTIVES

3.1 Primary Objectives

1. To evaluate the efficacy (based on FEV₁ improvement) and safety (based on development of AKI) of standard colistin TID dosing²⁴ versus PK-adjusted BID colistin dosing in adult CF subjects being treated for APE.
2. To evaluate the efficacy and safety of PK-adjusted BID colistin dosing versus standard tobramycin once daily dosing (8-10 mg/kg once daily) in adult CF subjects being treated for APE.
3. To evaluate the efficacy and safety of standard colistin TID dosing versus standard tobramycin once daily dosing in adult CF subjects being treated for APE.

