5. CRITERIA FOR EVALUATION

5.1 Primary Endpoints

1. Absolute change in FEV₁ % predicted with standard colistin TID dosing versus PK-adjusted colistin BID dosing, with APE treatment.
2. Absolute change in FEV₁% predicted with standard tobramycin daily dosing versus PK-adjusted colistin BID dosing, with APE treatment.

3. Absolute change in FEV1% predicted with standard tobramycin daily dosing versus standard colistin TID dosing, with APE treatment.
4. Safety of standard colistin TID dosing versus PK-adjusted colistin BID dosing in APE treatment, based on assessments of clinical symptoms, AKI occurrences during treatment (based on KDIGO criteria), change in urine protein:creatinine ratios, and an FDA approved renal injury biomarker test, Nephrocheck®, which measures: TIMP2 and IGFBP-7 (Astute Medical).
5. Safety of standard tobramycin daily dosing versus PK-adjusted colistin BID dosing or standard colistin TID dosing in APE treatment, based on assessments described in #4.

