8.4.2 Specific drug treatment arms

Standard colistin arm: Subjects initially receive IV colistin 2.5 mg/kg/d divided into three times daily (TID) dosing (Perrigo Company) ^{1,15, 24}. Previous literature has supported upward dose titration to minimize the incidence of side effects associated with parenteral administration¹⁵. Subjects receiving colistin will undergo a 2 day up-titration of dose to an ultimate dose of 4-5 mg/kg/day, for a total treatment of 14 days¹⁵. The drug is infused over 30 minutes on a TID dosing schedule. There are no pharmacokinetic measurements to guide standard dosing; however, plasma, sputum, and urine will be collected and analyzed from the subjects in this treatment arm on the same schedule as the modified colistin arm to serve as study controls. Treatment is currently guided by evidence of neurotoxicity or nephrotoxicity, based on clinical exam and on serum and urine studies.

Modified colistin arm Subjects receiving IV colistin undergo a 2 day up-titration to a maximum dose of 5 mg/kg/day, divided into twice daily (BID) dosing, for a total treatment of 14 days. The drug is infused over 30 minutes BID. Steady state plasma concentrations on visit 2 (generally at the 2nd-3rd dose once at goal dosing) will be measured; specifically, colistin peak (30-60 minutes after infusion), midpoint (4-6 hours after infusion) and/or trough (30-0 minutes prior to next infusion). A steady state sputum sample will be procured at visit 2 to assess epithelial lining concentrations, unless subjects are on inhaled colistin as this will create inaccuracies in colistin sputum concentration measurements. Processing of sputum for colistin measurements will be performed by the standardized method for processing sputum developed by CF Therapeutic Development Network ^{33,34}. A baseline and steady state urine samples will also be collected. Levels of colistin A and B and pro-drug from plasma, sputum, and urine (following processing) will be quantified within 36 hours to allow for measurement and interpretation. [name] will determine the optimal dose and intervals for APE subjects based on PK modeling with feedback from the PI, treating physician, and the National Jewish Health | Saint Joseph Hospital inpatient pharmacists. Colistin concentrations in plasma, sputum, and urine will be re-assessed at visit 3, after PK adjusted optimal dosing of colistin has reached a steady state.

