15.4 Sample size and power: The original power calculations estimated 90 subjects per arm in order to achieve power to demonstrate efficacy, or higher FEV₁ in a tobramycin versus colistin study arm. Since preliminary data demonstrates that colistin is safer than tobramycin in terms of kidney injury, the more appropriate power calculation would evaluate colistin superiority for safety. In a retrospective cohort 500 subjects, FEV1% improvement after tobramycin treatment during exacerbation therapy was 3% higher than in those receiving colistin; however, rates of acute kidney injury (rise in serum creatinine ≥ 0.3 mg/dL while on therapy) were 60% higher in tobramycin treated subjects versus standard colistin treated subjects. Since no preliminary data was available on less frequent colistin dosing, which theoretically would lead to less frequent episodes of kidney injury, we estimate we are powered to identify a safer method for dosing colistin with samples of 30 subjects per group, though we may be underpowered to find a significant FEV₁ difference between groups.

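### Section 15.4 and the synopsis call 30 per group powered to find a safer colistin regimen, but at the documented AKI rates the colistin-versus-colistin comparison has under 80% power even if PK-adjusted dosing abolishes AKI

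*Combined protocol and SAP*

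**What the plan says.** Section 15.4 mentions an FEV1-based estimate of 90 per arm, sets it aside, and argues that the calculation should concern safety instead. It then concludes: "we estimate we are powered to identify a safer method for dosing colistin with samples of 30 subjects per group". The synopsis repeats this under its rationale for the number of subjects. The same sentence admits that "no preliminary data was available on less frequent colistin dosing", and its only caveat on power is about FEV1.

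AKI is part of the primary safety endpoints in Section 5.1, defined there by KDIGO criteria. Section 3.1 makes PK-adjusted against standard colistin the first primary objective. The second is "To evaluate the efficacy and safety of PK-adjusted BID colistin dosing versus standard tobramycin once daily dosing", and the third is standard colistin against tobramycin.

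The AKI rates are in Section 1.1. In the retrospective cohort, "the incidence of AKI was 19% for the tobramycin group and 12% for the colistin group", with an odds ratio of 3.6 for tobramycin after adjustment for prior-year admissions. In the 16-subject pilot, "Two subjects experienced SCr rises of" at least 0.3 mg/dL.

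**The concern.** That one sentence is the whole case for 30 per group. A reader will take it to mean that the trial has an adequate chance of showing that one way of giving colistin harms the kidney less than another, particularly as the authors concede weakness for FEV1 and not for AKI.

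The effect size quoted beside it, AKI 60% more frequent on tobramycin, belongs to a different contrast (19/12 = 1.58, tobramycin against standard colistin). With a background rate near 12%, 30 subjects yield about 30 × 0.12 = 3.6 events, which leaves little room to show a reduction. If the claim stays, a non-significant AKI result could be read as evidence of no safety difference from an adequately sized trial.

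**Working it through.** **The plan's own figure.** There is no calculation to reproduce. I looked for a documented pair of rates that leads to 30 per group, using the usual normal approximation for 80% power:

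n = [1.96·√(2p̄(1−p̄)) + 0.8416·√(p₁(1−p₁) + p₂(1−p₂))]² / (p₁−p₂)²

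- 12% vs 0%: (1.96 × 0.3359 + 0.8416 × 0.3250)² / 0.12² = 0.868 / 0.0144, so 61 per arm.
- 12% vs 6%: 356 per arm.
- 19% vs 12%: 419 per arm.

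None gives 30.

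**Inputs.** 30 per arm (Section 15.4). Two-sided 0.05 (Section 15.2). Standard colistin 12% or 2/16 = 12.5%, and tobramycin 19% (Section 1.1). PK-adjusted colistin: no rate is given, so 0%, 3% and 6% are assumed, 0% being the best case possible.

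**Method.** Exact enumeration:

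Power = Σₐ Σ_b Bin(a; 30, p₁) · Bin(b; 30, p₂) · 1[p-value(a, b) ≤ 0.05]

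I did this for Fisher's exact test, the pooled chi-square without continuity correction, and the unadjusted likelihood-ratio test.

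**Best case, by hand.** If PK-adjusted AKI is 0%, that arm always shows 0/30, and power is the chance that the other arm reaches the critical count.

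- Likelihood ratio: 2/30 gives p = 0.092 and 3/30 gives 0.038, so at least 3 events are needed.
- Chi-square: 3/30 gives 0.076. For 4/30, z = 0.1333 / √(0.0667 × 0.9333 × 2/30) = 2.07, p = 0.038, so at least 4.
- Fisher: 5/30 gives 0.052 and 6/30 gives 0.024, so at least 6.

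With X ~ Bin(30, 0.12), P(X≥3) = 71.5%, P(X≥4) = 49.3% and P(X≥6) = 14.3%. At 12.5% these become 74.2%, 52.7% and 16.4%.

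**All contrasts, 30 per arm**

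| Contrast | AKI rates | Fisher | Chi-square | Likelihood ratio |
|---|---|---|---|---|
| PK-adjusted vs standard colistin | 0% vs 12% | 14% | 49% | 72% |
| | 0% vs 12.5% | 16% | 53% | 74% |
| | 3% vs 12% | 7% | 26% | 35% |
| | 6% vs 12% | 3% | 13% | 17% |
| PK-adjusted colistin vs tobramycin | 0% vs 19% | 52% | 85% | 94% |
| | 3% vs 19% | 30% | 57% | 61% |
| | 6% vs 19% | 17% | 35% | 38% |
| Tobramycin vs standard colistin | 19% vs 12% (crude) | 5% | 12% | 13% |
| | 32.9% vs 12% (OR 3.6) | 38% | 50% | 54% |

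The last row applies the cohort's adjusted odds ratio to 12%: 0.12/0.88 = 0.1364; × 3.6 = 0.4909; 0.4909/1.4909 = 32.9%. The crude odds ratio is (0.19/0.81)/(0.12/0.88) = 1.72, so the two versions of this contrast differ a good deal.

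**How the tests behave.** Over common rates of 0.5-50%, the largest true type I error is 2.7% for Fisher, 5.5% for chi-square and 8.9% for the likelihood ratio. Fisher therefore understates power and the likelihood ratio flatters it.

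**Break-even.** The standard-colistin rate needed for 80% power (Fisher / chi-square / likelihood ratio) is about 25 / 18 / 14% if PK-adjusted AKI is 0%, 32 / 26 / 25% if it is 3%, and 37 / 33 / 32% if it is 6%.

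**Precision.** Newcombe 95% half-widths for the risk difference are about 15-17 points (12% vs 0-6%), 16-18 points (19% vs 0-6%) and 19 points (19% vs 12%). Wald intervals give 12-14, 14-16 and 18, which is too narrow near 0%.

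**The case against.** Several points on the other side are fair.

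- **The trial's AKI rate may be higher.** The pilot reports "Mean colistin dosing was 3.42 mg/kg/d over 15 days", while the standard arm in Section 8.4.2 titrates "to an ultimate dose of 4-5 mg/kg/day". The trial endpoint uses KDIGO criteria, whereas the source rates use a 0.3 mg/dL creatinine rise. The 12.5% is also imprecise (exact 95% interval for 2/16: 1.6-38%). At 20% vs 0%, power would be 57 / 88 / 96%. But the documents project no such rate, and at 20% vs 6% power is still 20 / 39 / 41%.
- **The colistin arms may exceed 30.** Subjects unable to take tobramycin are randomised between the two colistin arms only. At 35 per arm, 12% vs 0% gives 24 / 62 / 81%, so one test passes 80%. The statement under review is about 30 per group, however, and within a total of 90 this would leave 90 − 70 = 20 on tobramycin.
- **The planned analysis is covariate-adjusted logistic regression.** The figures here are unadjusted benchmarks, with the likelihood ratio the nearest analogue. The documents do not give enough for an adjusted calculation of the colistin contrast. An arm with no events would also cause separation in that model.
- **80% is a convention**, and the documents state no target. That stands, but 3-17% under a halving of AKI is not powered by any usual standard.
- **Safer covers more than AKI.** Clinical symptoms, urine protein:creatinine and Nephrocheck also belong to the safety endpoints. They have no planning inputs and are not tested here.

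A reader might go further and infer that the plan contains a miscalculation, or that every safety contrast is underpowered whatever the truth. The documents support neither. No calculation is printed, so none is wrong, and PK-adjusted colistin against tobramycin passes 80% by chi-square and likelihood ratio if PK-adjusted AKI is zero.

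**Conclusion.** The point holds for AKI incidence, PK-adjusted against standard colistin, at 30 per arm. Power falls short of 80% by all three two-sided tests at the documented 12-12.5% rate, even in the best case that PK-adjusted dosing leaves no AKI, and it is far lower under any partial reduction.

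This rests on four assumptions: the retrospective and pilot rates carry over to the trial, arms are equal with no dropout, tests are unadjusted, and the PK-arm rates are ours. The fault is an unsupported planning claim in the only sample-size rationale. It does not show that the trial should not run at this size.

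**What to change.** In Section 15.4 and the synopsis, delete the statement of being powered and replace it with text along these lines:

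> Thirty subjects per group do not give 80% power for the AKI comparison between the colistin regimens at the available rates. Unadjusted benchmark power (two-sided 0.05; Fisher, conservative / chi-square / likelihood ratio, liberal; PK-arm rates assumed) is: PK-adjusted vs standard colistin, 3 / 13 / 17% (6% vs 12%) to 14 / 49 / 72% (0% vs 12%); PK-adjusted colistin vs tobramycin, 17 / 35 / 38% (6% vs 19%) to 52 / 85 / 94% (0% vs 19%); tobramycin vs standard colistin, 5 / 12 / 13% at the crude rates (19% vs 12%), or 38 / 50 / 54% if the cohort's adjusted odds ratio of 3.6 is applied to 12%. AKI rates in the trial may differ from the retrospective and pilot rates because of dose and the KDIGO definition, and colistin-only entrants may make the colistin arms larger than 30.

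If precision is quoted as well, use the Newcombe half-widths (about 15-17, 16-18 and 19 points), not Wald values.

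The cost is a wording change in two places and a less favourable stated power. Enrolment and treatment do not change.

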16. DATA COLLECTION, RETENTION AND CLINICAL MONITORING

16.1 Data Collection Instruments

The investigator will prepare and maintain adequate and accurate source documents designed to record all observations and other pertinent data for each subject who is enrolled in the study.

Study personnel will enter data from source documents corresponding to a subject's visit into the protocol-specific electronic Case Report Form (eCRF) when the information corresponding to that visit is available. Subjects will not be identified by name in the study database or on any study documented to be collected by the Sponsor (or designee), but will be identified by a subject number and initials.

If a correction is required for a CRF, the time and date stamps track the person entering or updating CRF data and create an electronic audit trail.

The Investigator is responsible for all information collected on subjects enrolled in this study. All data collected during the course of this study must be reviewed and verified for completeness and accuracy by the Investigator.

16.2 Data Management Procedures

Study subjects will not be identified by name in the study database or on any data capture screens but will be identified by initials and a unique subject identification number. Only study personnel will be able to link the study ID to the subject's name. The study coordinator will be responsible for data processing, in accordance with

procedural documentation. Database lock will occur once quality assurance procedures have been completed. All procedures for the handling and analysis of data will be conducted using good computing practices for the handling and analysis of data for clinical trials.

All study visits will occur in the context of regular clinical care. Data will be entered and stored in REDCap (Research Electronic Data Capture), a secure web-based application that supports data capture for research studies. A system of computerized data validation checks will be implemented and applied to the database on a regular basis. REDCap is able to log all user activity and all pages viewed by every user. It is capable of monitoring data entry, exporting data, modifying a field, running a report, or add/modifying a user, among a plethora of other activities. Administrators to be able to determine all the activity and all the data viewed or modified by any given user.

16.3 Security and Archiving of Data

Within REDCap, user controls limit access to various functionalities, such as being able to export data, to enter data, to add or modify database fields or survey questions, and to view the logging records.

To secure data, all user- submitted data in REDCap is filtered for any possibly harmful markup tags (e.g. <script>) and is then escaped before ever being displayed on a web page within the application. SQL queries sent to the database server from REDCap are all properly escaped before being sent. If any values used in an SQL query originated from user-defined values, they would have already been sanitized beforehand as well, as described above. User-defined data used within SQL queries also have their data type checked to prevent any mismatching of data types (e.g. making sure a number is really a number). These processes of sanitization, filtering, data type checking, and escaping all help to protect against methods of attack, such as Cross-Site Scripting (XSS) and SQL Injection. To specifically protect against Cross-Site Request Forgery (CSRF), which is another method of attack, REDCap utilizes a "nonce" (a secret, user-specific token) on every web form used in the application. The nonce is generated anew on each web page as the user navigates within REDCap during a session.

Robust password procedures, consistent with 21 Part 11, and physical security procedures are in place to prevent unauthorized personnel physical access to the server rooms.

Network accounts are password protected and maintained and monitored by the National Jewish Health Information Technology group. Data is backed up regularly according to the Information Technology's group procedures.

16.4 Availability and Retention of Investigational Records

The investigator must make study data accessible to the monitor, other authorized representatives of the Sponsor (or designee), IRB/IEC, and Regulatory Agency (e.g., FDA) inspectors upon request. A file for each subject must be maintained that includes the signed Informed Consent, HIPAA Authorization, and copies of all source

documentation related to that subject. The Investigator must ensure the reliability and availability of source documents from which the information on the CRF was derived.

All study documents (e.g. patient files, signed informed consent forms, copies of CRFs, Essential Documents and Study Reference Binders) must be secured for a period of 2 years following completion of the study. There may be circumstances for which the Sponsor is required to maintain study records and, therefore, the Sponsor should be contacted prior to removing study records for any reason.

16.5 Monitoring

The Investigator grants permission to the Sponsor (or designee), and appropriate regulatory authorities to conduct on-site monitoring and/or auditing of all appropriate study documentation, if needed. Monitoring visits may be conducted by representatives of the Sponsor according to the U.S. CFR 21 Part 312 and ICH Guidelines for GCP (E6) and to ensure investigator compliance to 21 CFR Parts 50, 56 and 312 and to GCP.

